4.2 Concomitant therapy restrictions

4.2.1

Concurrent cancer therapy, including chemotherapy, radiation therapy, immunotherapy, or biologic therapy can **NOT** be administered to patients while on this study. The use of alternative or complementary therapies is discouraged.

4.2.2

Radiotherapy is not permitted.

4.2.3

Filgrastim (G-CSF) may be used at the treating physician's discretion in patients with severe neutropenia (i.e. ANC <500/µL) to enhance neutrophil recovery when clinically indicated (for culture proven bacteremia or invasive fungal infections). Prophylactic or routine use of filgrastim in clinically well patients awaiting count recovery is not recommended.

4.2.4

Corticosteroid therapy is permissible only for the treatment of increased intracranial pressure or physiologic replacement. The lowest dose consistent with good medical management should be used. Corticosteroids should **NOT** be used as an antiemetic due to their effect on the blood brain barrier. Patients on steroids who require an increase in steroid dose for worsening neurologic symptoms should have an MRI performed within **5 days** to rule out tumor progression.

4.2.5

Appropriate antibiotics, blood products, anti-emetics, fluids, electrolytes and general supportive care are to be used as necessary. PCP prophylaxis is recommended following the institutional guidelines when absolute lymphocyte count is below 1200.

4.2.6

Anticonvulsants may be administered as clinically indicated. However, it is recommended to avoid enzyme inducing anticonvulsants.

For Supportive Care Guidelines use Children's Oncology group guidelines, see: https://members.childrensoncologygroup.org/prot/reference_materials.asp under Standard Sections for Protocols.

4.3 Pegylated interferon Administration

Pegylated interferon will be administered weekly (**+/- 5 days**) at a dose of 1mcg/kg/dose via subcutaneous injection, approximately at the same time every week.

It is important to rotate the injection sites. Teaching will be done to the parents/guardian/patient in the first and/or second injection so the family will learn the technique and can continue to do it at home. Family/guardian will be provided with diaries to document compliance and side effects.

Patients may be pre-medicated with acetaminophen or ibuprofen. Specifically, patients can receive acetaminophen 10-15 mg/kg (maximum 650 mg per dose, maximum dose 4 grams/24 hours) or ibuprofen 10 mg/kg within 1 hour prior to receiving PEPegylated interferon. The patients can continue on either acetaminophen or ibuprofen for up to 48 hours after the pegylated interferon injection as needed. The maximum dose of ibuprofen in a 24-hour period will be 40 mg/kg or patients with weight for more than 45 kg is 2.4 grams/24 hours. Premedication is optional.

Pegylated interferon will begin a Cycle on Day 1 if **ANC \geq 1,000/ μ L, platelet count \geq 100,000/ μ L** (transfusion independent).

Dose calculations should be based on actual weight and adjusted as necessary prior to each cycle.

The maximum dose is 150 mcg.

Note: The calculated dose should be rounded to the nearest highest 5mcg of the prescribed dose for convenience of administration. Each cycle is 28 days. The total duration of the trial is 2 years a total of 26 cycles.

See Section 5.0 for Dose Modifications Based on Toxicities.

The therapy delivery maps (TDMs) for this cycle are on the next pages

Following completion of the first cycle, the Pegylated interferon cycle is repeated weekly for up to a total of 26 cycles, as tolerated and in the absence of disease progression (see Section 10.4 for Response Evaluation). If disease progression occurs, the patient will be taken off protocol therapy.

Subsequent Pegylated interferon cycles should begin on Day 29 or when ANC \geq 1,000/ μ L, platelet count \geq 100,000/ μ L (transfusion independent), whichever occurs later.

Therapy Delivery Plan

Pegylated interferon Dose 1mcg/kg/dose 4 consecutive weeks (28 days) will constitute one cycle. This therapy delivery map relates to all cycles of Pegylated interferon
	
Patient Name: _____ DOB _____

--	---

Criteria to start a cycle: ANC ≥ 1,000/μL and platelet count ≥ 100,000/μL (transfusion independent). This cycle lasts 28 days.

DRUG	ROUTE	DOSAGE	DAYS	IMPORTANT NOTES	OBSERVATIONS
Pegylated interferon	SQ	1 mcg/kg/dose Max dose is 150 mcg/dose	weekly (+/-5 days)	Premed with Tylenol or ibuprofen as needed.	a. CBC with differential b. CMP, Magnesium, Phosphorous, Calcium, Uric Acid. c. PT/PTT d. Urinalysis e. Performance Score f. Hx, PE, Neuro Exam, Wt, Ht, VS. g. pregnancy test h. Assessment of clinical toxicity/ adverse events i. QOL questionnaire j. MRI of brain and/or spine k. Am Cortisol, Free T4, TSH. l. Ophthalmology Evaluation m. Pegylated interferon Diary n. lumbar puncture (See section 7.1) OBTAIN OTHER STUDIES AS REQUIRED FOR GOOD PATIENT CARE

Cycle- 28 Days (+/- 5)	Date Due	Date Given	Chemotherapy Dose	Studies
1				a-i, k, l, o
				a, b, e, f, h, m
2				a, b, e, f, h, m

Cycle- 28	Date Due	Date Given	Chemotherapy Dose	Studies
3				a, b, e, f, h, m
4				a, b, d, e, f, h, i, j, m, n
5				a, b, e, f, h, m
6				a, b, e, f, h, l, k, m
7				a, b, d, e, f, h-j, m, n
8				a, b, e, f, h, m
9				a, b, d, e, f, h, m
10				a, b, d, e, f, h-j, m, n
11				a, b, e, f, h, m
12				a, b, e, f, h, k, l, m

Cycle- 28				
Cycle- 28 Days (+/- 5)	Date Due	Date Given	Chemotherapy Dose	Studies
13				a, b, d, e, f, i, j, m, n
14				a, b, e, f, h, m
15				a, b, d, e, f, h, m
16				a, b, d, e, f, h-j, m, n
17				a, b, e, f, h, m
18				a, b, e, f, h, l, k, m
19				a, b, d, e, f, h-j, m, n
20				a, b, e, f, h, m
21				a, b, d, e, f, h, m
22				a, b, d, e, f, h-j, m, n

Cycle- 28	Date Due	Date Given	Chemotherapy Dose	Studies
23				a, b, e, f, h, m
24				a, b, d, e, f, h, i, k, l, m
25				a, b, d e, f, h- j, m, n
26				a, b, e, f, h, m
END of therapy				

a- Obtain weekly. If patient develops grade 4 neutropenia, CBCs should be checked **every 3 to 4 days** until recovery to grade 3.

n-Obtain prior to starting cycle one only for females of childbearing potential. For the rest of the protocol follow institutional policies about pregnancy testing.

j-Obtain after every third cycle and as clinically indicated. MRI of spine obtain at same time points as brain MRI, for patients with known or suspected spinal disease.

See Section 5.0 for Dose Modifications for Toxicities

For supportive care guidelines see:

http://members.childrensoncologygroup.org/prot/reference_material.asp

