3.2 INCLUSION CRITERIA

3.2.1 Age

Patients must be older than 3 years and less than or equal to 25 years of age at the time of enrollment

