4.1 Overview of the treatment plan

Treatment with pegylated interferon alpha-2b must begin within 14 days of patient enrollment. Patients may be pre-medicated as needed with acetaminophen 10-15 mg/kg (maximum 650 mg per dose) or ibuprofen 10 mg/kg within 1 hour of receiving Pegylated interferon. The patients can continue on either acetaminophen or ibuprofen for up to 48 hours after Pegylated interferon injection. The maximum dose of ibuprofen in a 24-hour period will be 40 mg/kg. Ibuprofen for Adolescents and Adults the maximum daily dose: 2.4 grams in 24 hours. Premedication is optional.

Each cycle of therapy will consist of pegylated interferon alfa-2b administered subcutaneously once weekly (**+/- 5days**) for 4 weeks for up to 2 years. Each dose should be administered on the same day

each week. There will be no breaks between cycles. Total number of cycles 26. Each dose is 1µg/kg subcutaneously. Nursing staff will instruct the patients or their caregivers regarding sites of injection and injection technique. Teaching needs to be documented. Rotating the sites of injection is strongly recommended.

Patients and/or their caregivers will be asked to maintain a diary (Appendix 5) documenting the dose of pegylated interferon alpha-2b given, site of administration and any side effects. This diary will be reviewed at each clinic visit. Patients will return to the Aflac clinic prior to start next cycles.

Doses could be rounded up to the nearest upper 5mcg for easier administration. For patients whose weight is greater than 150kg the maximum dose of Pegylated interferon to be administered is 150mcg/dose/ week.

MRI brain and /or spine will be performed as a baseline within **30 days** of enrollment and subsequently every 3 cycles.

See section 7.1 for required observations prior to start therapy.

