4.4 Criteria for Starting Subsequent Courses of Treatment

A course may be repeated every 28 days, up to a total of 2 years if the patient has at least stable disease and has again met laboratory parameters.

Patients who complete a treatment cycle may receive another cycle if:

- Disease Status: the patient has no evidence of progressive disease or in the opinion of the investigator, the patient is benefiting from the therapy with pegylated interferon alfa-2b) as evidenced by a decrease in tumor-related symptoms.
- Toxicity: the patient has not experienced any toxicity that meets off-study criteria as described in Section 5.0
- Patients will not be allowed to have a dose escalation after dose reduction due to toxicity.

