5.0 DOSE MODIFICATIONS FOR TOXICITY

For patients who are unable to tolerate the protocol-specified dosing schedule, dose adjustments are permitted in order to keep the patient on study drug. If administration of Pegylated interferon must be interrupted because of unacceptable toxicity, drug dosing will be interrupted or modified according to rules described below. Toxicity will be assessed using the NIH-NCI Common Terminology Criteria for Adverse Events, version 5.0

https://ctep.cancer.gov/protocoldevelopment/electronic_applications/docs/CTCAE_v5_Quick_Reference_5x7.pdf

Pegylated interferon dose level modification guidelines

Patients who experience significant toxicity as listed in section 5.0 will have the dose reduced by 25% of the dose on subsequent cycles. Two dose reductions are allowed, as long as there is no evidence of progressive disease (see section 10.4) Patients who again experience dose modifying toxicity after 2 dose reductions will be taken off protocol therapy.

Dose Modification for Toxicity	Dose and schedule
Standard dose	1mcg/kg/dose
Dose Modifications	First Dose Modification: reduction by 25% of dose
	Second Dose Modification: reduction by 50% of dose
	Permanently discontinue if unable to tolerate second dose modification

*For patients whose weight is greater than 150kg, the maximum dose of Pegylated interferon to be administered is 150mcg/dose/week. (See table above)

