5.1 Non-hematological Toxicities

The dose of Pegylated interferon will be reduced for any of the following toxicities at least possibly attributed to Pegylated interferon

- Any Grade 4 non-hematological toxicity
- Any Grade 3 non-hematological toxicity with the specific exclusion of:

- Grade 3 nausea and vomiting controlled by antiemetics
- Grade 3 fever or infection
- Grade 3 fever, myalgias, arthralgias, and rigors.
- Grade 3 hypophosphatemia, hypokalemia, hypocalcemia or hypomagnesemia responsive to oral supplementation.

- Any Grade 2 non-hematologic toxicity that persists for > 3 days and is considered sufficiently medically significant or sufficiently intolerable by patients that it requires treatment interruption
- Any other adverse event attributed to Pegylated interferon that requires treatment interruption for > 3 days or which recurs upon drug re-challenge and requires treatment interruption.
- Non-hematological toxicity that causes a delay of more than 14 days between treatment cycles.

Patients who experience non-hematologic toxicity should have appropriate laboratory testing at least weekly until the toxicity has resolved.

If the toxicity does not return to less or equal than Grade 1 within **14** days, the patient will no longer be eligible to receive treatment on this study.

If the toxicity returns to less or equal to Grade 1 within 14 days, the patient may restart the study drug at initial dose modification once weekly and remain at that dose.

If the same Grade 3 or 4 non-hematologic toxicity recurs, hold drug and wait until toxicity returns to less or equal to Grade 1. If toxicity returns to less or equal to grade 1 within 14 days, the patient may restart the study drug at second dose modification and remain at that dose. If the toxicity does not return to less than Grade 1 within **14** days, the patient will no longer be eligible to receive treatment on this study.

If the same Grade 3 or 4 non-hematological toxicity recurs and it is felt to be due to the study drug, the patient will no longer be eligible to receive pegylated interferon alfa-2b.

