Administration: Pegylated interferon will be administered subcutaneously once weekly, on the same day each week. Rotating sites. **Guidelines for administration:**

Education to the parents/patient and or caregivers will be provided on how to measure and draw the adequate amount of medication and subcutaneous administration will be taught to the family. Keep refrigerated. Procedures for proper handling and disposal of hazardous/anticancer drugs should be considered.

Adverse reactions reported with INTERFERON ALFA (Package insert)

CNS: neurologic deficits, headache, decreased mental status, dizziness, impaired memory, impaired concentration, paresthesia, confusion, change in taste or smell, irritability, insomnia, anxiety, change in behavior, visual disturbance, seizures, gait disturbances, hallucinations, encephalopathy, psychomotor retardation, coma, stroke, transient ischemic attacks

Psychiatric: agitation, manic behavior, psychotic reactions, depression, suicidal ideation
Flu-like symptoms: fatigue, myalgia, arthralgia, fever, chills, asthenia, sweating, leg cramps, malaise

Gastrointestinal: nausea, vomiting, diarrhea, anorexia, abdominal pain, flatulence, impaired digestion, gingival bleeding, pancreatitis, colitis, gastrointestinal hemorrhage, stomatitis, abdominal fullness, hypermotility, hepatitis, dysphasia

Skin: injection site reaction, alopecia, hair change, rash, dry skin, pruritus, hematoma, psoriasis, eczema, seborrhea, bruising

Pulmonary: dryness or inflammation of the oropharynx, epistaxis, rhinitis, sinusitis, coughing, dyspnea, pneumonitis

Cardiovascular: rhythm disturbances, chest pain, hypotension, hypertension

Laboratory: neutropenia, thrombocytopenia, anemia, elevated liver function tests, proteinuria.

Other: conjunctivitis, menstrual irregularity, syncope, sexual dysfunction, coagulopathy, weight loss, night sweats, thyroid dysfunction, diabetes

Frequency of Side Effects of Pegylated Interferon

Likely or Common Happens to 21 to 100 children out of every 100	Less Likely or Occasional Happens to 5 to 20 children out of every 100	Rare but Serious, Happens to less than 5 children out of every 100.

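### The round-up to 5 mcg does not exempt toxicity-reduced doses, and applied to them it cancels the first 25% cut for children above 13.33 to 15.0 kg

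*Combined protocol and SAP*

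**What the plan says.** The full dose is 1 mcg/kg weekly, based on actual weight and updated before each cycle (Section 4.3). Rounding appears in two places. Section 4.3 is advisory: "The calculated dose should be rounded to the nearest highest 5mcg of the prescribed dose for convenience of administration". Section 4.1 is permissive: "Doses could be rounded up to the nearest upper 5mcg for easier administration". The direction is upward in both, and neither limits the rule to the full dose.

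The reductions are in Section 5.0. A patient with significant toxicity "will have the dose reduced by 25% of the dose on subsequent cycles", and the table there lists "First Dose Modification: reduction by 25% of dose", then a 50% reduction as the second step. Section 5.0 says nothing about rounding. After recovery from non-hematologic toxicity, Section 5.1 says that "the patient may restart the study drug at initial dose modification once weekly and remain at that dose". Section 4.4 adds: "Patients will not be allowed to have a dose escalation after dose reduction due to toxicity".

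On who could be affected, Section 3.2.1 says: "Patients must be older than 3 years and less than or equal to 25 years of age at the time of enrollment". No minimum weight is given.

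**The concern.** A dose of 0.75 mcg/kg times weight is also a calculated dose, so the wording of Section 4.3 covers it. In a small child a 25% cut is less than 5 mcg, and rounding up in 5 mcg steps can then return the reduced dose to the full one. The protocol would require a reduction and, by another of its rules, undo it. A small child with, say, a Grade 4 non-hematologic toxicity could restart at the dose that preceded it while being counted as dose-reduced. Only two reductions are allowed before removal from therapy, so an empty step also uses up one of them.

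**Working it through.** The plan gives no figure for a rounded or reduced dose, so there is nothing of its own to reproduce.

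**Inputs.** Full dose 1 mcg/kg on actual weight and round-up to 5 mcg (Section 4.3); first reduction 25% and second 50% (table in Section 5.0). I take both reductions from the standard 1 mcg/kg dose.

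**Formulas.** For weight w in kg, with each dose rounded up to the next multiple of 5 mcg:
- full = 5 × ceil(w / 5)
- first reduction = 5 × ceil(0.75w / 5)
- second reduction = 5 × ceil(0.50w / 5)

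**Two worked cases.**
- 14 kg: full 14 → 15; first 10.5 → 15; second 7 → 10. The first cut is zero, and the child stays at 15/14 = 1.07 mcg/kg instead of 0.75.
- 12 kg: full 12 → 15; first 9 → 10; second 6 → 10. The second step adds nothing.

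**Bands.** The first dose rounds to 15 rather than 10 once 0.75w exceeds 10, that is, above 10/0.75 = 13.33 kg.

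| Weight (kg) | Full (mcg) | First (mcg) | Second (mcg) | First cut |
|---|---|---|---|---|
| above 10 to 13.33 | 15 | 10 | 10 | 33.3% |
| above 13.33 to 15.0 | 15 | 15 | 10 | 0% |
| above 15 to 20 | 20 | 15 | 10 | 25% |
| above 20 to 25 | 25 | 20 | 15 | 20% |
| above 26.67 to 30 | 30 | 25 | 15 | 16.7% |

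**Why the first cut is never zero above 15 kg.** Write the full dose as 5k, so w ≤ 5k. The cut is zero only if 0.75w exceeds 5(k − 1). Since 0.75w is at most 3.75k, this needs 3.75k > 5k − 5, so k < 4. The full dose is then at most 15 mcg, and w at most 15 kg. A search in 0.01 kg steps up to 150 kg agrees: above 10 kg, full and first doses coincide only from 13.34 to 15.00 kg, and first and second only from 10.01 to 13.33 kg.

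**If reduced doses are not rounded up.** 14 kg gives 15, 10.5 and 7 mcg, and 12 kg gives 15, 9 and 6 mcg. Each step is then a real reduction.

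**The case against.** The best reply is that the text largely settles the matter. Rounding is there for convenience and is optional in Section 4.1, while the reductions in Sections 5.0 to 5.2 are mandatory. The rounding note in Section 4.3 sits with the 1 mcg/kg instruction and is followed by a pointer to Section 5.0. A site that gives 10.5 mcg breaches nothing, and a careful pharmacist would not round a reduced dose back to the one that caused toxicity.

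Other controls help. The diary records each dose and is reviewed at clinic visits, and the therapy delivery map has a dose entry for each cycle. Each cycle needs adequate neutrophil and platelet counts, and restart after non-hematologic toxicity needs recovery to Grade 1 or less. The unchanged dose is 1.00 to 1.12 mcg/kg (15/15 to 15/13.4), at the low end of the 1 to 3 mcg/kg used in the craniopharyngioma series cited in Section 2.7.1.

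Most of this stands, and it limits the likelihood and the harm. It does not remove the point. Section 4.3 says that rounding should be done, a reduced dose falls within its wording, and no sentence exempts it. The records would show an unchanged 15 mcg only to someone who compares entries. A tolerable mcg/kg figure in other patients does not excuse a missed reduction in one who has just had significant toxicity.

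A reader might go further and infer that the first cut vanishes for every child above 10 to 15.0 kg, because 15 × 0.75 = 11.25 also rounds up to 15. That requires rounding the full dose, cutting the rounded figure and rounding again. No text directs this. Section 4.3 calculates from actual weight, and the table in Section 5.0 sets the reductions under a standard dose stated per kg. The wider band should not be used.

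**Conclusion.** The point holds as a minor, conditional patient-safety defect. The stated rounding rule, applied as worded, gives no first reduction above 13.33 to 15.0 kg and no additional second reduction above 10 to 13.33 kg. In both bands the second dose, 10 mcg, is still below the full 15 mcg.

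This rests on four assumptions: the site rounds reduced doses up; the percentage is taken from the unrounded weight-based dose; the second step is 50% of the standard dose; and eligible children weigh more than 10 kg. The documents give no weights. With about 20 patients enrolled (Section 9.1), possibly none is both in these bands and in need of a reduction.

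A reader might also infer that the toxic-event count in Section 9.6 is distorted, since an empty step could leave a child counted after only one real reduction. That would need this chain of conditions and further dose-modifying toxicities in the same child. Nothing in the documents shows that it would happen often enough to matter, and it does not touch the response endpoint. The effect on trial results is negligible.

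**What to change.** Add to Section 5.0, with cross-references in Sections 4.1 and 4.3:
1. Reduced doses are calculated as 0.75 or 0.50 mcg/kg times actual weight.
2. The 5 mcg round-up applies only to the full 1 mcg/kg dose.
3. A reduced dose may be rounded only to the nearest volume that can be measured reliably at the vial strength used, provided each step is lower than the dose last given.

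Rounding reduced doses down to 5 mcg would not be enough. At 12 kg, 9 and 6 mcg both become 5 mcg, and the two steps merge again.

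The drafting cost is small; the practical cost is in preparation. Under Section 6.1, families draw up doses at home ("Education to the parents/patient and or caregivers will be provided on how to measure and draw the adequate amount of medication"), and odd doses are harder to measure. At 14 kg the first reduced dose of 10.5 mcg is 10.5/100 = 0.105 mL at the 100 mcg/mL PEG-Intron strength, but 10.5/400 = 0.026 mL at the weakest SYLATRON strength (40 mcg per 0.1 mL). A suitable vial strength must therefore be chosen for small children, and item 3 allows rounding to a measurable volume.

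The cut from the delivered dose can also exceed 25% where the full dose was rounded up: 30% at 14 kg (15 to 10.5 mcg), 43% at 15.1 kg (20 to 11.3 mcg) and 49.5% at 10.1 kg (15 to 7.6 mcg). The sponsor should accept this knowingly. The reduced dose is still the intended 0.75 mcg/kg.

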4.4 Criteria for Starting Subsequent Courses of Treatment

A course may be repeated every 28 days, up to a total of 2 years if the patient has at least stable disease and has again met laboratory parameters.

Patients who complete a treatment cycle may receive another cycle if:

- Disease Status: the patient has no evidence of progressive disease or in the opinion of the investigator, the patient is benefiting from the therapy with pegylated interferon alfa-2b) as evidenced by a decrease in tumor-related symptoms.
- Toxicity: the patient has not experienced any toxicity that meets off-study criteria as described in Section 5.0
- Patients will not be allowed to have a dose escalation after dose reduction due to toxicity.

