5.2 Hematologic Toxicity

The dose of Pegylated interferon will be reduced for any of the following toxicities:

- Grade 4 decreased neutrophil count (neutropenia) > 5 days duration
- Grade 4 decreased platelet count (thrombocytopenia) > 5 days duration
- ≥ 2 platelet transfusions per cycle for platelet counts < 30,000/ μ L
- ≥ 14 day delay in starting subsequent cycles due to low ANC (< 1,000/ μ L or low platelet count (less than 100,000/ μ L.)

Patients who experience hematologic toxicity should have appropriate laboratory testing at least weekly until the toxicity has resolved.

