8.0 CRITERIA FOR REMOVAL FROM PROTOCOL THERAPY AND OFF STUDY CRITERIA

8.1 Criteria for Removal from Protocol Therapy

- Progressive disease (see definition in Section 10.4).
- Significant toxicity at least possibly attributed to Pegylated interferon despite two dose reductions (as stated in Section 5.0).
- Refusal of further protocol therapy by patient/parent/guardian.
- Completion of 26 cycles of protocol therapy.
- Physician determines it is in patient's best interest.
- Development of a second malignancy.
- Patient becomes pregnant while on study.

Patients who are off protocol therapy are to be followed until they meet the criteria for Off Study (see below). Follow-up data will be required unless consent was withdrawn.

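### Section 4.4 lets a patient with progressive disease receive further cycles, against 4.3, 8.1 and 10.4; separately, 9.4 sets no cut-off at progression for counting a response

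*Combined protocol and SAP*

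**What the plan says.** Section 4.4 (Criteria for Starting Subsequent Courses of Treatment) opens with a condition: "A course may be repeated every 28 days, up to a total of 2 years if the patient has at least stable disease", provided the laboratory parameters are met again. The disease-status bullet below it sets a different one. Another cycle may be given when "the patient has no evidence of progressive disease or in the opinion of the investigator, the patient is benefiting from the therapy", and the evidence of benefit is a lessening of symptoms from the tumor.

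Other sections bear on treatment after PD:
- Section 4.3: "If disease progression occurs, the patient will be taken off protocol therapy".
- Section 5.0: "Two dose reductions are allowed, as long as there is no evidence of progressive disease".
- Section 8.1 lists PD as a reason for removal from protocol therapy and points to 10.4 for its definition.
- Section 10.4 states that clinical or radiographic PD after any cycle ends the study drug.

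On counting responses:
- Section 9.4 defines a responder as a patient whose best overall response is CR or PR, reached at any point on study. A response followed by PD still counts. The reverse order is not addressed.
- Under 8.1 and 8.2, patients off therapy are still followed, and PD is not an off-study criterion.
- Section 9.2 stops the trial at 0 responders of 9 and calls the drug promising at 3 or more of 17. It also lists SD as a response, alongside CR and PR.

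**The concern.** The two halves of the 4.4 bullet are joined by an or. A child whose scan meets the PD definition, but who has fewer symptoms, may therefore continue under the bullet and must stop under 4.3, 8.1 and 10.4. No section says which rule takes precedence, and 4.4 is where a clinician would look when deciding on the next cycle. Two investigators acting in good faith could treat the same child differently.

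The second issue is about analysis. If such a child later shrinks to PR, 9.4 read literally makes that child a responder, although EFS under 9.3.1.2 has already dated the failure at PD. Section 9.5 refers to both responses and progressions as the basis for decisions but does not say how this order is handled. With a go threshold of 3 responders, a single patient can matter.

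**Working it through.** **1. Whom the second branch reaches.** The first branch admits every patient without PD. The second therefore changes the outcome only for a patient with PD. Because it requires symptoms to have lessened, a patient with clinical PD would not ordinarily qualify. It mainly reaches radiographic PD with symptomatic improvement.

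**2. The rules side by side, for a patient with PD.**
- 4.4 opening sentence: no further cycle (at least SD required).
- 4.4 bullet: further cycle permitted on the investigator's judgment.
- 4.3, 8.1, 10.4: removal or no further drug, with no exception stated.
- 5.0: dose reductions presuppose no PD, which fits the stricter rule.

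Section 10.4 also asks that worsening neurological symptoms be separated from other causes before removal. That is about confirming PD and does not permit treatment after it.

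**3. Exposure at stake.** Inputs: 26 cycles of 4 weekly doses (4.1, 4.3); first MRI at the end of cycle 3, then scans before cycles 4, 7, 10, 13, 16, 19, 22 and 25 (7.1). For PD at the first MRI:
- Under 4.3, 8.1 and 10.4: 0 further cycles.
- Under the bullet: at most 26 − 3 = 23 cycles, or 23 × 4 = 92 doses, with 8 − 1 = 7 more scheduled MRIs.

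**4. The plan's design figures.** Inputs from 9.2: n1 = 9, r1 = 0, n = 17, r = 2, response rates 5% and 25%.
- Early termination at 5%: 0.95^9 = 0.630 (stated 0.63).
- Expected sample size at 5%: 9 + (1 − 0.630) × 8 = 11.96 (stated 11.96).
- P(go | p) = sum over x = 1 to 9 of b(x; 9, p) × P(Y ≥ 3 − x), with Y binomial(8, p). This gives 0.0466 at 5% and 0.8122 at 25%, against the stated 5% alpha and 80% power.

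All four reproduce.

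**5. Effect on the decisions.** One patient with PD followed by a counted response changes 0/9 (stop) to 1/9 (continue), or 2/17 (not promising) to 3/17 (promising). The bullet is the main scheduled route to such a response, because it keeps the patient on drug and on the three-cycle MRI schedule. After removal, 7.1 asks for one off-therapy scan and 7.2 sets no MRI schedule.

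**6. How much shrinkage would be needed.** Assume one target lesion that has just reached the PD threshold. PR is measured from baseline: a fall of at least 65% in the three-diameter product, or at least 50% in the two-diameter product (10.7). PD is a rise of 40% or 25% respectively. If PD is also measured from baseline:
- 3D: 1 − 0.35/1.40 = 75%.
- 2D: 1 − 0.50/1.25 = 60%.

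If PD is measured from the smallest product since treatment began (10.7), with that nadir a fraction m of baseline, the fall is 1 − 0.35/(1.40m) in 3D and 1 − 0.50/(1.25m) in 2D. At m = 0.75 these are 67% and 47%. Section 10.4 first refers both response and progression to the pre-study baseline, then defines PD by comparing the baseline scan with the best-response scan (also in 2.8). The documents do not settle which reference governs. None of these falls applies to PD by a new lesion or to clinical PD.

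**The case against.** The strongest reply is that the bullet is one permissive clause against several mandatory ones, including the sentence that opens its own section. A careful reader would follow the mandatory text, and no section outside 4.4 supports treatment past PD. This limits the weight of the point but does not remove it: the clause has no function except to admit patients with PD, and no order of precedence is given.

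Several stronger readings are tempting, and the documents do not support them:
- **That the dose rules contradict each other in their own right.** Section 5.1 says "The dose of Pegylated interferon will be reduced for any of the following toxicities at least possibly attributed to Pegylated interferon", and 5.2 uses the same mandatory form, while 5.0 allows reductions only without PD. These clash only if the bullet has already overridden 4.3, 8.1 and 10.4. Otherwise no patient with PD is on drug.
- **That 9.4 contradicts the EFS definition.** It does not. Section 9.4 already accepts patients who are responders and also have an EFS event. It gives a permissive rule without a cut-off.
- **That the type I error is inflated.** The documents give no rate of response after PD in these tumors, so any inflated figure would merely restate an assumption. The one example, in 2.6, is a predominantly cystic craniopharyngioma that grew and then responded completely. It is a different tumor, and the size of the increase is not given.
- **That a response to some later therapy would count.** Section 9.4 classifies best response for the purpose of judging treatment effect, which argues against it.
- **That only a modest shrinkage is needed after PD.** That requires both the 10.7 nadir reference and a nadir already close to PR.

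It is also fair to say that 9.2, by listing SD as response, could count a patient with SD before PD without any later shrinkage. That is a reason to align 9.2 with 9.4.

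**Conclusion.** The contradiction in 4.4 is real and should be fixed. Its second branch permits dosing that the section's opening sentence, 4.3, 8.1 and 10.4 exclude. For PD at the first MRI the gap is 0 further cycles against 23 (92 doses). The latter is a ceiling that needs symptomatic benefit to be judged present before every cycle for nearly two years; no realistic value can be derived.

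The missing cut-off in 9.4 is a separate gap in the analysis rule. Read literally, it would count a response after PD on continued drug, and one such patient could reverse either decision. The fall required from the PD threshold is 75% (3D) or 60% (2D) for a single target lesion with PD referenced to baseline, and less under the nadir reference. The frequency is unknown. The stated design stands: alpha 4.7%, power 81.2%, early termination 0.63. Overall weight is low to moderate.

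**What to change.** - **Section 4.4:** delete the second branch of the disease-status bullet, from the word or through the reference to reduced tumor symptoms. The bullet then agrees with the opening sentence and with 4.3, 5.0, 8.1 and 10.4.
- **Section 9.4:** add a sentence such as: *For the 0/9 and 3/17 decisions, best overall response (CR or PR) is taken from assessments up to and including the first PD; any later shrinkage is described but not counted, and EFS is dated at first PD.*
- **Section 9.2:** align its definition of response with 9.4 (CR or PR). Without this the cut-off does not work, since SD before PD could already count.

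The cost is amendment wording, with no extra patients, visits or data. There are two downsides. A genuine late response after apparent progression would not count toward the go decision. A child with symptomatic benefit despite PD could not continue on protocol, but 4.3, 8.1 and 10.4 already require that. If the sponsor does want the exception, it has to be written into 4.4's opening sentence, 4.3, 5.0, 8.1 and 10.4, and the 9.4 sentence is still needed.
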